### **11.3. Decision to Withdraw or Terminate Subject's Participation Prior to Study Completion**

The Sponsor-Investigator can decide to withdraw a subject(s) from Investigational Product and/or other protocol-required therapies, protocol procedures, or the study as a whole at any time prior to study completion.

Subjects may be eligible for continued treatment with Aadi Bioscience's Investigational Product and/or other protocol-required therapies by a separate protocol or as provided for by the local country's regulatory mechanism.

## **12. REGULATORY OBLIGATIONS**

### **12.1. Informed Consent**

The Informed Consent Document must be reviewed and approved by the Sponsor-Investigator, Aadi Biosciences, and the IRB prior to use. Updates to the informed consent document are to be communicated to Aadi Bioscience prior to submitting for IRB review and approval. For research participants who do not speak and/or read English, a short-form consent should be used. The short form is used to document that the elements of informed consent were orally presented to the research participant by a qualified interpreter. Both the short form and a written summary, which may also be the IRB-approved English-language informed consent document, must be submitted filed in the subject chart.

Before a subject's participation in the clinical study, the investigator is responsible for obtaining written informed consent from the subject after adequate explanation of the aims, methods, anticipated benefits, and potential hazards of the study and before any protocol-specific screening procedures or the IP is administered.

The acquisition of informed consent is to be documented in the subject's medical records, and the informed consent form to be signed and personally dated by the subject and by the person who conducted the informed consent discussion. The original signed informed consent form is to be retained in accordance with institutional policy, and a copy of the signed consent form is to be provided to the subject.

If a potential subject is illiterate or visually impaired, the investigator must provide an impartial witness to read the informed consent form to the subject and must allow for questions. Thereafter, both the subject and the witness must sign the informed consent form, per institutional policy, to attest that informed consent was freely given and understood.

### **12.2. Institutional Review Board/Independent Ethics Committee**

A copy of the protocol, informed consent form, other written subject information, and any proposed advertising material must be submitted to the IRB for written approval. A copy of the written approval of the protocol and informed consent form must be received by Aadi Bioscience before recruitment of subjects into the study and shipment of Aadi Bioscience IP.

The Sponsor-Investigator must submit and, where necessary, obtain approval from the IRB for all subsequent protocol amendments and changes to the informed consent document. The Sponsor-Investigator is to notify the IRB of reportable deviations from the protocol or SAEs occurring at the site and other AE reports received from Aadi Bioscience, in accordance with local procedures.

The Sponsor-Investigator is responsible for obtaining annual IRB approval [IRBs only]/renewal [IRBs and IECs] throughout the duration of the study. Copies of the Sponsor-Investigator's reports and the IRB continuance of approval must be sent to Aadi Bioscience.

### **12.3. Subject Confidentiality**

The Sponsor-Investigator must ensure that the subject's confidentiality is maintained for documents submitted to Aadi Bioscience.

- Subjects are to be identified by a unique subject identification number.
- Where permitted, date of birth is to be documented and formatted in accordance with local laws and regulations.
- On the CRF demographics page, in addition to the unique subject identification number, include the age at time of enrollment.
- For SAEs reported to Aadi Bioscience, subjects are to be identified by their unique subject identification number, initials (for faxed reports, in accordance with local laws and regulations), and date of birth (in accordance with local laws and regulations).
- Documents that are not submitted to Aadi Bioscience (e.g., signed informed consent forms) are to be kept in confidence by the investigator, except as described below.

In compliance with Federal regulations/ICH GCP Guidelines, it is required that the Sponsor-Investigator and institution permit authorized representatives of the company, of the regulatory agency(s), and the IRB direct access to review the subject's original medical records for verification of study-related procedures and data. Direct access includes examining, analyzing, verifying, and reproducing any records and reports that are important to the evaluation of the study. The investigator is obligated to inform and obtain the consent of the subject to permit such individuals to have access to his/her study-related records, including personal information.

#### **12.4. Protocol Amendments**

If Sponsor-Investigator amends the protocol, agreement from Aadi Bioscience must be obtained. The IRB must be informed of all amendments and give approval. The Sponsor-Investigator must send a copy of the approval letter from the IRB to Aadi Bioscience.

#### **12.5. Termination of the Study**

Both Aadi Bioscience and the Sponsor-Investigator reserve the right to terminate the Sponsor-Investigator's participation in the study according to the study contract. The Sponsor-Investigator is to notify the IRB in writing of the study's completion or early termination and send a copy of the notification to Aadi Bioscience.

## **13. DATA HANDLING AND RECORDKEEPING**

### **13.1. Data/Documents**

The Sponsor-Investigator must ensure that the records and documents pertaining to the conduct of the study and the distribution of the investigational product are complete, accurate, filed, and retained. Examples of source documents include: hospital records; clinic and office charts; laboratory notes; memoranda; checklists; dispensing records; recorded data from automated instruments; copies or transcriptions certified after verification as being accurate copies; microfiche; x-ray film and reports; and records kept at the pharmacy; and the laboratories, as well as copies of CRFs or CD-ROM.

### **13.2. Data Management**

Data will be collected via CRF and entered into the clinical database. These data will be electronically verified through use of programmed edit checks specified by the clinical team. Discrepancies in the data will be brought to the attention of the clinical team, and investigational site personnel, if necessary. Resolutions to these issues will be reflected in the database. An audit trail within the system will track all changes made to the data.

### **13.3. Responsibilities for Data Collection**

The Sponsor-Investigator is responsible for complying with the requirements for all assessments and data collection (including subjects not receiving protocol-required therapies) as stipulated in the protocol for each subject in the study. For subjects who withdraw prior to completion of all protocol-required visits and are unable or unwilling to continue the Schedule of Assessments (in Table 3, the investigator can search publicly available records (where permitted) to ascertain survival status.

This ensures that the data set(s) produced as an outcome of the study is/are as comprehensive as possible.

### **13.4. Sample Storage and Destruction**

Any blood or tumor sample collected can be analyzed for any of the tests outlined in the protocol and for any tests necessary to minimize risks to study subjects. This includes testing to ensure analytical methods produce reliable and valid data throughout the course of the study. This can also include, but is not limited to, investigation of unexpected results, incurred sample reanalysis, and analyses for method transfer and comparability.

All samples and associated results will be no less than single coded prior to being shipped from the site for analysis, or storage. Tracking of samples will be independent of the subject's identification number for the study. Results are stored in a secure database to ensure confidentiality.

Results from this analysis are to be documented and maintained but are not necessarily reported as part of this study.

The records should be retained by the Sponsor-Investigator according to ICH, local regulations, or as specified in the Clinical Trial Agreement, whichever is longer; but at a minimum, all study documentation must be retained for 2 years after the last marketing application approval in an

ICH region or after at least 2 years have elapsed since formal discontinuation of clinical development of nab-Sirolimus.

Since the evaluations are not expected to benefit the subject directly or to alter the treatment course, the results of other exploratory studies are not placed in the subject's medical record and are not to be made available to the subject, members of the family, the personal physician, or other third parties, except as specified in the informed consent.

The subject retains the right to request that the sample material be destroyed by contacting the Sponsor-Investigator. Following the request from the subject, the Sponsor-Investigator is to provide the sponsor with the required study and subject number so that any remaining blood or tumor samples and any other components from the cells can be located and destroyed. Samples will be destroyed once all protocol-defined procedures are completed.

The Sponsor-Investigator is the exclusive owner of any data, discoveries, or derivative materials from the sample materials and is responsible for the destruction of the sample(s) at the request of the subject, at the end of the storage period, or as appropriate (e.g., the scientific rationale for experimentation with a certain sample type no longer justifies keeping the sample). The subject has no commercial rights to such product and has no commercial rights to the data, information, discoveries, or derivative materials gained or produced from the sample.

## **14. QUALITY CONTROL AND QUALITY ASSURANCE**

### **14.1. Study Monitoring**

Institutional support of trial monitoring will be in accordance with the FHCC/University of Washington Cancer Consortium Institutional Data and Safety Monitoring Plan. Under the provisions of this plan, FHCC Clinical Research Support (CRS) coordinates data and compliance monitoring conducted by consultants, contract research organizations, or FHCC employees unaffiliated with the conduct of the study. Independent monitoring visits occur at specified intervals determined by the assessed risk level of the study and the findings of previous visits per the institutional DSMP.

In addition, protocols are reviewed at least annually and as needed by the Consortium Data and Safety Monitoring Committee (DSMC), FHCC Scientific Review Committee (SRC) and the FHCC/University of Washington Cancer Consortium Institutional Review Board (IRB). The review committees evaluate accrual, adverse events, stopping rules, and adherence to the applicable data and safety monitoring plan for studies actively enrolling or treating subjects. The IRB reviews the study progress and safety information to assess continued acceptability of the risk-benefit ratio for human subjects. Approval of committees as applicable is necessary to continue the study.

The trial will comply with the standard guidelines set forth by these regulatory committees and other institutional, state and federal guidelines.

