**Table 2 - Day 1 Only Dosing Levels (Amendment 3, Version 4.0 and Later Only)**

Dose Levels (Day 1 Only Dosing)	Planned Starting Dose of ABI-009 in mg/m 	Planned Starting Dose of Pazopanib in mg
-2C	15	400
-1C	20	400
0C	30	400
1C	45	400
2C	60	400
3C	75	400
4C	100	400

After enrollment of the first 3 dose cohorts (0, -1, and -2) an RP2D had not yet been identified. DLTs were observed in all three of these enrolled cohorts. A total of 16 subjects were consented resulting in 13 enrollments and 3 screen failures. DLTs were observed at all dose levels. A summary of DLTs observed in Cohorts 0, -1, and -2 are provided below in Table 3. Of the 13 subjects enrolled, 11 subjects had nab-Sirolimus and/or pazopanib dose reduced, and three subjects discontinued due to toxicity.

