### **3. STUDY POPULATION**

#### **3.1. Number of Subjects**

**Phase 1:** up to 49 subjects to identify the MTD, but the MTD may be reached with as few as 22 subjects. Subjects who discontinue from the study prior to completing the DLT assessment window for reasons other than toxicity will be replaced at the same dose level.

**Phase 2:** In the first stage, at least 23 subjects would be enrolled, including the 3-6 subjects from phase 1 at the RP2D. If at least 11 were progression-free at the 3 months evaluation, then additional subjects would be enrolled to a total of 39 subjects in the Phase 2.

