### **6.4. Dose Limiting Toxicity**

Dose-limiting toxicities will be assessed in the first 2 cycles (2, 3-week cycles).

A DLT is defined as any Grade 3 or greater AE, at least possibly related to either or both nab-Sirolimus and pazopanib. Only toxicities with a clearly identified and documented alternative explanation may be deemed non-DLT. Dose-limiting toxicities include any death not clearly due to underlying disease or extraneous causes, or persistent intolerable nonhematologic AE of any grade that requires dose reduction or permanent discontinuation of the study-drug, in the opinion of the investigator.

The following adverse events may be excluded from being considered a DLT:

- Grade 3 nausea/vomiting or diarrhea for less than 72 hours, with adequate antiemetic and other supportive care;
- Grade 3 fatigue for less than 1 week;
- Grade 3 or higher electrolyte abnormality that lasts up to 72 hours, is not clinically complicated, and resolves spontaneously or responds to conventional medical interventions.
- Lab abnormalities that have no clinical sequelae (e.g. febrile neutropenia from low ANC, bleeding from thrombocytopenia, etc.) and resolve to grade 1 or better within 7 days will not be considered a DLT.

Nab-Sirolimus dose modification guidelines are outlined in Table 9 and Table 11 for clinically significant toxicities that are deemed related to nab-Sirolimus.

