### 9.2. Safety Analysis

The safety analysis set includes all treated subjects.

Safety and tolerability will be monitored through continuous reporting of treatment emergent and TRAEs, AEs of special interest, laboratory abnormalities, and incidence of subjects experiencing dose modifications, dose delay/dose not given, dose interruptions, and/or premature discontinuation of IP due to an AE. All AEs will be recorded by the investigator from the time the subject signs informed consent until 30 days after the last dose of protocol therapy. Adverse events will be graded by NCI CTCAE v5.0.

Physical examination, vital signs, laboratory assessments (e.g., serum chemistry, hematology), and ECOG performance status will be monitored and reviewed per institutional standards. All SAEs (regardless of relationship to IP) will be followed until resolution. Local laboratory analysis will be performed as per study schedule.

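### The protocol sets no count-based toxicity trigger for phase 2, although DLT clearance of the RP2D can rest on 0 of 3 or 1 of 6 subjects

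*Combined protocol and SAP*

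**What the plan says.** **Monitoring.** Section 14.1 places oversight under an institutional data and safety monitoring plan. It says "protocols are reviewed at least annually and as needed" by the DSMC and other bodies, and that "The review committees evaluate accrual, adverse events, stopping rules, and adherence to the applicable data and safety monitoring plan". It adds: "Approval of committees as applicable is necessary to continue the study". No count, rate or number of subjects is attached to any of this.

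**Safety analysis.** Section 9.2 states: "Safety and tolerability will be monitored through continuous reporting of treatment emergent and TRAEs". It sets no threshold.

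**Phase 1.** Section 2.3 contains the only count-based toxicity rules. Two or more DLTs close a dose level, and the MTD is the highest dose with at most 1 of 6 (or 0 of 3) subjects having a DLT. Section 6.4 fixes the window: "Dose-limiting toxicities will be assessed in the first 2 cycles".

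**Phase 2.** Sections 3.1 and 9.5 describe a Simon two-stage design with at least 23 subjects in stage 1, "including the 3-6 subjects from phase 1 at the RP2D", and 39 evaluable subjects in total. The stage 1 decision uses progression-free status at 3 months only. Subjects without a follow-up scan are replaced.

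**Target DLT rate.** Section 2.3 gives it as at most 20% in its opening paragraph and as roughly 17% in the MTD definition. The synopsis also gives roughly 17%.

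**Rules titled as stopping rules.** Sections 6.1.2, 6.1.3 and 6.2.2 hold or discontinue drug in an individual subject. They do not act on enrollment.

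**The concern.** Once the RP2D is named, DLT counts have no pre-specified consequence for the trial. The Simon interim cannot fill the gap, because it counts progression: a dose that is active but too toxic passes it.

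The amount of DLT information behind the RP2D is small. A 3+3 is built to choose a dose quickly, and its 3 to 6 subjects cannot exclude a DLT rate well above the protocol's own target. Most RP2D subjects will be treated in phase 2, where better information accrues, and the plan does not say what level of toxicity would prompt a second look.

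Toxicity is a live issue for this combination. In the first three cohorts, "DLTs were observed in all three of these enrolled cohorts", 11 of 13 subjects had a dose reduced and three stopped for toxicity. Table 3 lists 17 DLT occurrences, of which 8 were platelet decreases. Laboratory DLTs of that kind need not surface as serious adverse events: Section 10.4.1 leaves even some grade 4 laboratory findings to the investigator's judgment. SAE reporting therefore does not substitute for a running DLT count.

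**Working it through.** **Inputs from the protocol.** Clearance at 0/3 or at most 1/6, and target rates of roughly 17% and at most 20% (Section 2.3); 23 subjects in stage 1 and 39 in total, including 3 to 6 from phase 1 (Sections 3.1 and 9.5); a two-cycle DLT window (Section 6.4).

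**Assumptions.** True DLT rates of 20% to 50% are scenarios. The look times and counts in step 4 are an illustration. Subjects are treated as independent.

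**1. The plan's own figures.** 1/6 = 16.7%, which is the stated rate of roughly 17%. An exact minimax search for 50% versus 70%, alpha 0.10 and power 90% returns 23 and 39, so the phase 2 size also reproduces.

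**2. What phase 1 clearance establishes.** A dose with true DLT rate p clears with 0/3, or with 1/3 followed by 0/3:

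P(clear) = (1-p)^3 + 3p(1-p)^2 × (1-p)^3

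At p = 0.40 this is 0.216 + 0.432 × 0.216 = 0.216 + 0.093 = 0.309. At p = 0.20 it is 0.512 + 0.384 × 0.512 = 0.709. The same formula gives 0.494 at 30% and 0.172 at 50%.

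Exact (Clopper-Pearson) two-sided 95% upper limits:
- 0/3: 1 - 0.025^(1/3) = 0.708
- 1/6: the p that solves (1-p)^6 + 6p(1-p)^5 = 0.025, which is 0.641

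**3. Exposure after clearance.** New evaluable subjects number 39 - 6 = 33 to 39 - 3 = 36, plus replacements. At a true rate of 40%, 33 × 0.4 = 13.2 to 36 × 0.4 = 14.4 of them would be expected to have a DLT. No count in the protocol would be crossed.

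**4. What a trigger could do.** Take the reference rate as 20% and pause at cumulative RP2D counts of 5/12, 7/18, 8/23 or 11/31. The tail probabilities P(X ≥ k) at 20% are 0.073, 0.051, 0.072 and 0.033. A look at 39 is left out, because enrollment is then complete and nothing can be paused.

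The calculation starts from the cleared state (0 DLTs in 3, or 1 in 6). Between looks, add a Binomial(n - n_prev, p) number of DLTs. At each look, remove the probability at or above the boundary and sum what was removed.

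| True DLT rate | P(pause), from 0/3 | P(pause), from 1/6 |
|---|---|---|
| 20% | 5.0% | 5.6% |
| 30% | 30.2% | 29.8% |
| 40% | 69.7% | 67.2% |
| 50% | 93.6% | 91.9% |

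At 40%, the mean number treated would be 24.7 (from 0/3) or 26.1 (from 1/6) instead of 39, but only if every pause became permanent and the futility stop is ignored.

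**5. Sensitivity to the reference rate.** Choose each count as the smallest k with P(X ≥ k) ≤ 0.05. A 20% reference gives 6/12, 8/18, 9/23 and 11/31. A 1/6 reference gives 5/12, 7/18, 8/23 and 10/31. The choice between the two stated rates moves every boundary by one DLT.

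**The case against.** **Review is not absent.** As-needed committee review, required approval to continue, continuous adverse event reporting, SAE reports within 24 hours (Section 10.4.2), termination rights (Section 12.5) and the individual hold and discontinuation tables all exist. This stands. A reader might infer that phase 2 would run to completion whatever DLTs occurred; the documents do not support that. The means of pausing is there, and only a number that prompts it is missing.

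**Section 14.1 is institution-wide wording.** A reader might take its mention of stopping rules as a promise that the protocol breaks. It refers to protocols in general, and this protocol does contain rules a committee could evaluate: the 3+3 counts and the Simon count. The gap is an omission, not a contradiction.

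**The institutional plan may hold a count.** It may, and it cannot be seen. The finding is limited to what the protocol states.

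**The RP2D uses more than DLTs.** Section 2.3 bases it on all safety and efficacy data. Only DLT clearance at that dose rests on 3 to 6 subjects. The DLTs in the first three cohorts also came from Day 1/Day 8 dosing with pazopanib 800 mg, whereas new enrollment is Day 1 only with 400 mg. They show why toxicity deserves attention but do not estimate the rate at a future RP2D.

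**The 31% is easily misread.** It is the chance that one tested dose with a 40% rate clears its own cohort. It is not the chance that the RP2D has a 40% rate. A dose above the starting level must also be reached through the lower ones.

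**The saving in subjects is uncertain.** If the DSMC resumes enrollment, fewer are spared. The printed futility rule would by itself stop at 23 with probability 34% if 3-month PFS were 50%.

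**Conclusion.** The point holds as an omission: the protocol has no count-based toxicity trigger in phase 2, and 33 to 36 new subjects plus replacements can be treated at a dose whose DLT clearance is compatible with rates up to 64% or 71%. It is a worthwhile, low-cost improvement. It does not show that oversight is missing or that the phase 2 dose will be too toxic.

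The size of the benefit depends on the boundary chosen. With the illustrative counts, a true rate of 40% would prompt a pause about two times in three, and a true rate of 30% about three times in ten. The fall in mean subjects treated, from 39 to about 25-26 at 40%, is an upper bound on the saving and should not be quoted as the expected gain.

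These figures rest on a 20% reference rate, looks at 12, 18, 23 and 31 subjects with complete DLT windows, independent subjects, and a start from 0/3 or 1/6. If the institutional plan already contains a trigger, the remaining point is that the protocol should state or cite it.

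**What to change.** In Sections 9.2 and 14.1:

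1. Reconcile the two target DLT rates (at most 20% and roughly 17%) and name the one that serves as the reference.
2. Tally DLTs, by the Section 6.4 definition in Cycles 1-2, in all RP2D subjects from both phases.
3. Pre-specify the cumulative counts at which enrollment pauses for DSMC review, or cite the institutional rule if one exists. The counts in the working are one illustration; the sponsor should set its own.
4. State how subjects still inside the two-cycle window are handled at each look, and what the DSMC may decide after a pause.
5. Print the operating characteristics over a range of true DLT rates.

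**Cost.** Protocol wording and a running count. CTCAE grading and the Day 8 and Day 15 visits in Cycles 1 and 2 already supply the data. The illustrated set carries about a 5% chance of an unnecessary pause at a true rate of 20%, and short accrual holds are possible while the six-week DLT windows complete. Individual dosing rules are unaffected.
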